8.5 Reporting and Follow-Up of Pregnancies

8.5.1 Period of Collection and Follow-up

Pregnancies detected between the time of signature of the ICF and the time before first exposure to the IP will be considered a reason for screen failure. No pregnancy form will be filled in for that case, however the diagnosed pregnancy must be captured in the screen failure page of the CRF.

Any pregnancy detected after enrollment must be reported by the Investigator within 24 hours. This also includes pregnancies spontaneously reported to the Investigator after the end of the study for a subject. A dedicated pregnancy form will be used to report reportable cases of pregnancy.

Confidentiality Statement

Data and information contained in this document are considered to constitute trade secrets and confidential commercial information, and the legal protections provided to such trade secrets and confidential information are hereby claimed under the provisions of applicable law. No part of this document may be publicly disclosed without the written consent of Philip Morris Products S.A.

Any pregnancy that was potentially associated with exposure to IP (P4M3 and CIG) will be followed-up until an outcome is reached (e.g., normal delivery, spontaneous abortion, or voluntary termination), and until 8 weeks after delivery. Any pregnancy complication, adverse pregnancy outcome or maternal complications will be recorded as an AE accordingly.

The procedure outlined in Section 8.3 should be followed to collect pregnancy reports and provide any additional/follow-up information to Sponsor.

8.5.2 Reporting of Pregnancies

The Investigator is responsible for informing the responsible IEC of any pregnancy case that was reported during the study, as determined by local regulations.

8.6 Adverse Events Leading to Discontinuation

Subjects who are discontinued from the study because of an AE will undergo the early termination procedures (section 9.5), as soon as practical after discontinuation and will enter the 3-day Safety Follow-Up Period.

Any AEs or SAEs that are ongoing at the end of the Safety Follow-Up Period will be managed as described in section 8.2.6.

8.7 Investigational Product Malfunction and Misuse

Any occurrence of P4M3 product events, affecting P4M3 Battery Unit, P4M3 Cartridge, or MDEDR, including malfunction or misuse (use not in accordance with its label and instruction) by a subject will be documented by the Investigator. Information regarding P4M3 product events should be actively collected during the study and assessed for severity as Minor or Major:

Minor – Can be resolved easily.

Major – Cannot be resolved.

P4M3 product events will be categorized into: Break, Fluid Leak, Intermittent Loss of Power, Power Problem, Premature Indicator Activation or Other.

Investigational product misuse may result in use-related hazards (section 2.3.3).

Furthermore, any malfunction or misuse of P4M3 that leads to an AE/SAE will follow the same processes as described above.

Confidentiality Statement

Data and information contained in this document are considered to constitute trade secrets and confidential commercial information, and the legal protections provided to such trade secrets and confidential information are hereby claimed under the provisions of applicable law. No part of this document may be publicly disclosed without the written consent of Philip Morris Products S.A.

9 Study Activities

A detailed schedule of assessment can be found in [Appendix A](#). Measurements not conducted at the exact timepoint but conducted within the given time window (if applicable) do not constitute a protocol deviation but an accepted variability for the given timepoint.

In general, if no start time for the procedures is provided, then the procedure can be performed at any time during the day.

9.1 Screening Period

9.1.1 Screening Visit (Day -30 to Day -3)

The Screening visit will be performed ≤ 28 days prior to enrollment at Admission (Day -2). First, the ICF along with study information will be given to the subject. Prior to being asked to sign the consent form, subjects will be given time to review the study information and ask any questions. Once the ICF is signed and dated and timed, the screening procedures can be performed in the order deemed most practical. While it is recommended to complete as many screening procedures as possible in one day, it is permissible to complete those over more than one day. Smoking is allowed at the Screening visit.

Screening activities and examinations are listed in [Table 9](#).

Table 9 Time Schedule – Screening Visit

Time	Procedures	Additional Information
Start of Procedure	Screening Visit	
Prior to any other study procedure	Informed consent process and signature of ICF	
During the Visit	Information on risks of smoking, advice on smoking cessation	
	Inclusion/exclusion criteria	
	Smoking history	Tobacco/Nicotine Product Use History questionnaire
	ECG	
	Spirometry	
	Demographics	
	Medical History/ Concomitant Diseases	

Confidentiality Statement

Data and information contained in this document are considered to constitute trade secrets and confidential commercial information, and the legal protections provided to such trade secrets and confidential information are hereby claimed under the provisions of applicable law. No part of this document may be publicly disclosed without the written consent of Philip Morris Products S.A.

Time	Procedures	Additional Information
Start of Procedure	Screening Visit	
	Prior (≤ 4 weeks) and concomitant medication	
	Physical examination	
	Body height and weight/ BMI	
	Vital signs	
	Serology	HBV, HCV, and HIV
	Collection of blood sample	- Safety panel (hematology, clinical chemistry)
		- Pregnancy test (all female subjects)
	Collection of spot urine	- Safety panel
		- Drug test
		- Cotinine test
	Alcohol breath test	
	Review of eligibility criteria	
	P4M3 demonstration	Without product use
	Identification of current CIG brand	Explain CIG provision for confinement period by subject
	AE/SAE recording	

Abbreviations:

AE = Adverse event; BMI = Body mass index; CIG = Conventional cigarette(s); ECG = Electrocardiogram; HBV = Hepatitis B virus; HCV = Hepatitis C virus; HIV = Human immunodeficiency virus; ICF = Informed consent form; P4M3 = e-cigarette; SAE = Serious adverse event.

If the eligibility criteria are met, the investigational site staff will contact the subject to arrange Visit Day -2 at the site.

9.2 Baseline Period (Enrollment and Randomization)

9.2.1 Admission Day -2

Day -2 should be scheduled within 27 days after Screening visit ². The procedures of the Admission visit on Day -2 (Table 10) can be performed in order deemed most practical according to Table 10.

² Alternate subjects will have to repeat the Admission Day -2 visit to qualify for randomization. The data of that repeated visit will be captured in the database as "Admission Day -2 visit – Second occurrence".

Confidentiality Statement

Data and information contained in this document are considered to constitute trade secrets and confidential commercial information, and the legal protections provided to such trade secrets and confidential information are hereby claimed under the provisions of applicable law. No part of this document may be publicly disclosed without the written consent of Philip Morris Products S.A

Enrolment of a subject will take place at Day -2 only if all eligibility criteria are met, after confirmation of a negative pregnancy test (for female subjects only). The confinement period will start after the successful enrolment. All other procedures and data collection will be completed following the enrollment of the subject.

Table 10 Time Schedule – Admission Visit Day -2

Time	Procedures	Additional Information
Start of Procedure	Admission Visit Day -2	
Start of the visit	Check-in at site	CIG use will be allowed on site on Day -2
Prior enrolment	Collection of blood sample	- Pregnancy test
	Collection of spot urine	- Drug test - Cotinine test
	Alcohol breath test	
	Body weight	BMI calculation
	Vital signs	
	Smoking history	Tobacco/Nicotine Product Use History questionnaire
	Inclusion/exclusion criteria	
	Information on the risks of smoking, advice on smoking cessation, and briefing on P4M3	
Prior to breakfast	Enrollment	After confirmation of the eligibility of the subject
During the visit	Breakfast	
	Lunch	
	Detailed training on how to use P4M3	Subject can use P4M3 ad libitum for approximately 10 minutes per flavor
	Concomitant medication	
	Concomitant disease status	
	AE/SAE recording	
	P4M3 product events	
End of the visit	Subjects remain confined	11:00 PM stop of smoking

Abbreviations:

AE = Adverse event; BMI = Body mass index; CIG = Conventional cigarette(s); P4M3 = e-cigarette; SAE = Serious adverse event.

Confidentiality Statement

9.2.2 Baseline Visit Day -1

Baseline exams will be performed, and subjects will be randomized at Baseline Visit. Randomization will take place only for subjects who are willing to comply with study procedures and to use P4M3 or keep abstinent from smoking (SA) for at least 5 days. [Table 11](#) shows the assessments that will be performed at Baseline Visit Day -1.

Table 11 Time Schedule – Baseline Visit Day -1

Time	Procedures	Additional Information
Start of Procedure	Baseline Visit Day -1	
Prior to breakfast	Spirometry	
	Collection of blood sample	After ≥6 hours of fasting - Safety panel (hematology, clinical chemistry)
	Collection of spot urine	- Pregnancy test
	ECG	
	Vital signs	
	Concomitant medication	
	Start 24-hour urine collection	For Day -1
	COHb in blood CYP1A2 activity	Intake of caffeine tablet 6 hrs (±15 min) ahead of blood sample collection
Prior to randomization	Breakfast	
During the visit	Randomization	Per IxRS
	FTND	Questionnaire
	Concomitant medication	
	Concomitant disease status	
	AE/SAE recording	
	ABOUT–Product Experience	Questionnaire
	Subjects are informed of their assigned study arm	
Collection of CIG butts for accountability		
End of visit (11:00 PM)	CIG ad libitum consumption	Subject remains confined stop

Abbreviations:

ABOUT = Assessment of behavioral outcomes related to tobacco and nicotine products; AE = Adverse event; CIG = Conventional cigarette(s); COHb = Carboxyhemoglobin; CYP1A2 = Cytochrome P450 1A2; ECG = Electrocardiogram; FTND = Fagerström test for nicotine dependence; IxRS = Interactive web and voice response system; SAE = Serious adverse event.

Confidentiality Statement

Data and information contained in this document are considered to constitute trade secrets and confidential commercial information, and the legal protections provided to such trade secrets and confidential information are hereby claimed under the provisions of applicable law. No part of this document may be publicly disclosed without the written consent of Philip Morris Products S.A

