Provided that the 28-day Screening period is not exceeded, alternate subjects (not yet randomized) have to repeat the Admission visit of the following group to re-confirm their eligibility for randomization.

- Baseline (from Day -1, 06:30 AM until Day 1, 06:29 AM):

Subjects may continue smoking their CIG *ad libitum*, except before/during assessments requiring smoking breaks. The 24-hour urine collection for Day -1 will start in the morning of Day -1 (urine collection details provided in [Appendix A](#)). Baseline assessments will be performed as indicated in [Appendix A](#).

On Day -1, subjects will be randomized. Subjects will be informed about their randomized study arm by the study site staff on Day 1 prior to start of product use. The four randomization arms are:

- P4M3 CA35 arm: 18 subjects, *ad libitum* use of P4M3 using CA Cartridges
- P4M3 CM35 arm: 18 subjects, *ad libitum* use of P4M3 using CM Cartridges
- CIG arm: 18 subjects, *ad libitum* use of their own preferred CIG brand
- SA arm: 18 subjects who will abstain from CIG smoking

- Exposure period in confinement setting (from Day 1 until Day 5 11:00 PM, followed by Discharge at Day 6):

The exposure period in confinement consists of 5 days of *ad libitum* use of the assigned product in the P4M3 and CIG arms. Use of any TNP other than the assigned product will not be allowed and may, at the discretion of the investigator, result in the subject’s discontinuation from the study. Subjects allocated to the SA arm will be asked to abstain from CIG smoking.

Confidentiality Statement

Data and information contained in this document are considered to constitute trade secrets and confidential commercial information, and the legal protections provided to such trade secrets and confidential information are hereby claimed under the provisions of applicable law. No part of this document may be publicly disclosed without the written consent of Philip Morris Products S.A

Daily 24-hour urine will be collected from Day 1 to Day 5. On Day 1, product use must not start before the end of 24-hour urine collection of Day -1. The 24-hour urine collection period for Day 5 will end in the morning of Day 6 prior to Discharge.

During the confinement period, site staff will distribute assigned products to the subjects and record all products distributed in the source documentation.

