6.3 Method for Assigning Subjects to Study Arms

At the end of the Baseline period enrolled subjects will be randomized using an interactive web and voice response system (IxRS) on Day -1 at any time during the day. Subjects will be informed of their randomized study arm in the morning of Day 1, prior to 06:30 AM (the start of the exposure period). Subjects will be randomized (stratified by sex) to one of the four study arms (CA35, CM35, CIG, and SA) in a 1:1:1:1 ratio.

Quotas will be applied to ensure that the randomized subjects contain at least 40% of both sexes (males and females) per arm.

Any alternate subject that has not been randomized will enter the 3-day Safety follow-up period.

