6.4 Blinding

This is an open-label study; hence the subjects and PI(s) or designees will be unblinded to the subject's arm.

Confidentiality Statement

Data and information contained in this document are considered to constitute trade secrets and confidential commercial information, and the legal protections provided to such trade secrets and confidential information are hereby claimed under the provisions of applicable law. No part of this document may be publicly disclosed without the written consent of Philip Morris Products S.A.

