9.3 Randomized Exposure Period

9.3.1 Exposure in Confinement Period

On Day 1, subjects will be informed about their allocation to a study arm, i.e., either P4M3 CA35, P4M3 CM35, CIG, or SA. [Table 12](#) shows the assessments that will be performed at Day 1, 2, 3, 4, and 5; [Table 13](#) shows the assessments that will be performed at Day 6 ahead of the Discharge from confinement:

Table 12 Time Schedule – Day 1, 2, 3, 4, and 5

Time	Procedures	Additional Information
Start of Procedure	Day 1, 2, 3, 4, and 5	
Prior to breakfast	Vital signs	
	COHb in blood	
	Completion of Day -1 urine collection	
	Start of next 24-hour urine collection	Each day of the confinement period. Day 5 collection will be completed in the morning of Day 6, ahead of Discharge
	Day 1 only: Inform subjects on allocated study arm	
During the visit	Breakfast	
	Distribution of the P4M3 Battery Units and Cartridges to subjects in P4M3 arms	
	HPT	P4M3 arms only
	Day 5 only: CYP1A2 activity	Intake of caffeine tablet 6 hrs (\pm 15 minutes) ahead of the blood sample collection
	Concomitant Medication	
	Concomitant Diseases	
	AE/SAE recording	
	ABOUT–Product Experience	Questionnaire
	P4M3 product events, malfunctions/ misuse	P4M3 arms only
	End of visit (11:00 PM)	Collection of CIG butts
Cartridge/e-liquid use		Subjects remain confined

Abbreviations:

Confidentiality Statement

Data and information contained in this document are considered to constitute trade secrets and confidential commercial information, and the legal protections provided to such trade secrets and confidential information are hereby claimed under the provisions of applicable law. No part of this document may be publicly disclosed without the written consent of Philip Morris Products S.A

ABOUT = Assessment of behavioral outcomes related to tobacco and nicotine products; AE = Adverse event; COHb = Carboxyhemoglobin; CIG = Conventional cigarette(s); CYP1A2 = Cytochrome P450 1A2; HPT = Human puffing topography; P4M3 = e-cigarette; SAE = Serious adverse event.

At Day 6, following completion of the procedures and examinations (Table 13), the subjects will be discharged for the Safety follow-up period.

Table 13 Time Schedule – Discharge Day 6

Time	Procedures	Additional Information
Start of Procedure	Day 6	
Prior to breakfast	Collection of blood sample	After ≥ 6 hours of fasting 
 - Safety panel (hematology, clinical chemistry) - Pregnancy test (all female subjects)

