### 9.6.1.2 Main Analysis

The primary analysis will be a mixed model for repeated measures (MMRM) conducted with the PPS. An unstructured matrix will be used to model the variance-covariance structure within subjects. If this model fails to converge, then the following variance-covariance matrices will be used (in order) until one converges: Heterogeneous Toeplitz, Heterogeneous First Order Autoregressive, Heterogeneous Compound Symmetry, Variance Components, Compound Symmetry, and finally no repeated statement.

The model for the endpoint expressed on the log-scale will adjust for the endpoint value at baseline (log-scale), Day, randomization arm, and its interaction with Day, and sex. The model described above will be implemented in the SAS® language as:

```
PROC MIXED data=dataset method=reml nobound;
  class Arm Day Subject Sex;
  model Log(Endpoint) = Log(Baseline) Day Arm Arm*Day
    Sex / ddfm=kenwardroger2 solution;
  repeated Day / subject=Subject(Arm) type=un rcorr;
  lsmeans Arm*Day / pdiff cl;
  lsmestimate 'Contrast P4M3 (CA35 and CM35 combined) vs. CIG' exact syntax to be
adjusteddepending on the coding of class variables / cl upper alpha=0.025;
  lsmestimate 'Contrast P4M3 CA35 alone vs. CIG' exact syntax to be adjusted depending
on the coding of class variables / cl upper alpha=0.025;
  lsmestimate 'Contrast P4M3 CM35 alone vs. CIG' exact syntax to be adjusted depending
on the coding of class variables / cl upper alpha=0.025;
RUN;
```

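### Table 11 of the protocol has subjects told their arm on Day -1, against Day 1 everywhere else; a site following it would disclose allocation while the baseline 24-hour urine is still open

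*Protocol*

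**What the plan says.** **Disclosure.** Table 11, the time schedule for the Day -1 baseline visit, contains the row "Subjects are informed of their assigned study arm". It stands under the procedures done during the visit, after randomization, with no clock time and no note moving it to Day 1. Protocol 4.1 says instead: "Subjects will be informed about their randomized study arm by the study site staff on Day 1 prior to start of product use". Section 6.3 has subjects "informed of their randomized study arm in the morning of Day 1, prior to 06:30 AM", and 9.3.1 says "On Day 1, subjects will be informed about their allocation to a study arm".

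**Randomization.** Section 6.3 allows the IxRS allocation "on Day -1 at any time during the day", although the same sentence also places it at the close of the baseline period.

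**Baseline collection.** Protocol 4.1 runs the baseline period from 06:30 AM on Day -1 to 06:29 AM on Day 1. The 24-hour urine starts in the morning of Day -1, and Table 12 has it completed before breakfast on Day 1. Meanwhile, "Subjects may continue smoking their CIG" without limit except around assessments; Table 11 ends smoking at 11:00 PM.

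**Analysis.** The confirmatory repeated-measures model "will adjust for the endpoint value at baseline" on the log scale (SAP 9.6.1.2; Protocol 12.5.1.4).

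**The concern.** Baseline adjustment gives an unbiased comparison of arms only if the baseline value cannot have been influenced by allocation. Randomization secures that when the baseline is measured before the subject knows the arm. Under Table 11 it might not be. A subject told during Day -1 that cigarettes stop next morning for five days, or that they continue, could smoke more or less for the rest of that day. The change would enter the Day -1 urine and so the covariate. The MMRM would then correct for a baseline difference that allocation itself had produced.

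At stake is the size of the reported reduction for the urine biomarkers, which is the trial's headline result, together with the descriptive percent change from baseline.

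**Working it through.** **1. Where disclosure is placed.**

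| Place | Time of disclosure |
|---|---|
| Protocol Table 11 (9.2.2) | Day -1, during the visit, no clock time |
| Protocol synopsis, definition of Randomization, 4.1, 6.2.2; SAP 4.1 | Day 1, before product use |
| Protocol 6.3; SAP 4.6.1 | Day 1, before 06:30 AM |
| Protocol 9.3.1 and Table 12 | Day 1 only, before breakfast, listed after completion of the Day -1 urine |
| Protocol Appendix A; SAP 13.1 | One mark, under Day 1 |

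Table 11 is the only outlier. SAP 7, which lists changes from the protocol, does not mention it.

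**2. What each version does to the baseline.** Smoking is possible from 06:30 AM to 11:00 PM on Day -1, a span of 16.5 hours. With disclosure on the morning of Day 1, smoking has already stopped, and Protocol 4.1 bars product use until the Day -1 collection ends, so knowing the arm cannot alter the baseline. With disclosure during Day -1, any smoking between disclosure and 11:00 PM can be affected. The opening of Protocol section 9 lets a procedure without a start time be done at any time of day, so that interval could be most of the 16.5 hours.

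**3. Which endpoints are exposed.** Of the primary biomarkers, 3-HPMA, 2-CyEMA and total NNAL are measured in the 24-hour urine: three of four. All four key secondary biomarkers are urinary. Together that is seven of eight. COHb is a blood measure that Table 11 lists before breakfast, ahead of randomization.

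**4. The plan's own figure.** Protocol 12.9.4 states primary power of at least 99%, from a one-sided 2.5% two-sample t-test on the log scale with 30 against 15 subjects. In the least favourable row (3-HPMA, fourth planning study: GMR 52.86%, GCV 39.57%):

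- SD = √ln(1 + 0.3957²) = 0.381
- SE = 0.381 × √(1/30 + 1/15) = 0.1206
- noncentrality = 0.6375 / 0.1206 = 5.29 on 43 degrees of freedom
- power = 99.93%

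Multiplied over the four biomarkers, power is 99.90% in that study and above 99.99% in the other three. The stated figure reproduces, and no input to it depends on when the arm is disclosed.

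**5. Possible size of the bias (illustration only).** Let f be the P4M3/CIG ratio of baseline distortion and b the slope on log baseline. Assume Day 5 values are themselves unaffected by Day -1 smoking. The adjusted log-GMR is the outcome difference minus b times the baseline difference, so the reported GMR equals the true GMR × f^(−b). Neither f nor b is given in the documents.

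| f | b = 0.3 | b = 0.6 | b = 0.9 |
|---|---|---|---|
| 0.8 | 1.069 | 1.143 | 1.222 |
| 0.9 | 1.032 | 1.065 | 1.099 |
| 1.1 | 0.972 | 0.944 | 0.918 |
| 1.2 | 0.947 | 0.896 | 0.849 |
| 1.3 | 0.924 | 0.854 | 0.790 |

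A true 52.86% would be reported as 64.6% at one extreme (52.86 × 1.222) and 41.7% at the other (52.86 × 0.790). A true reduction of 47.1% would thus appear as 35.4% or 58.3%. At the unfavourable extreme, with the planning SD kept, power in this row would be 94% for the combined arms (30 against 15) and 86% for a single variant (15 against 15). Elsewhere in the grid it is higher.

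**The case against.** The strongest reply is that the intended design is not in doubt. Nearly every other statement puts disclosure on Day 1, section 9 refers the reader to Appendix A for the detailed schedule, and Table 12 places disclosure after the Day -1 urine is complete. On that view one stray row is a clerical slip. This stands to the extent that the risk arises only if a site follows Table 11. But Table 11 is the schedule a site would use on that day, and nothing in it corrects the row.

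Second, only smoking after disclosure can change. If half of Day -1 smoking remained and the biomarker moved in proportion (both assumptions), a 20% shift in the 24-hour value would need about 40% more smoking in that half (0.20 / 0.5). That makes the outer rows of the illustration unlikely, though not the mechanism.

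Third, success is a ratio below 1, and the planning ratios lie far below it, so the test is much less sensitive than the estimate. This stands.

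A reader might also infer that staff knowledge alone contaminates the baseline, since "the subjects and PI(s) or designees will be unblinded". The documents do not say when staff learn the arm, and on Day -1 every subject smokes their own cigarettes freely. No mechanism is described by which staff knowledge would change intake. Nor does the position of the FTND and product experience questionnaires below randomization in Table 11 establish a fault: untimed procedures are not a fixed sequence, and neither questionnaire is a model covariate.

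**Conclusion.** The point holds as an internal contradiction with a real, conditional risk of bias. If Table 11 is followed, the baseline covariate for seven of the eight confirmatory biomarkers could be affected by allocation. The effect on the adjusted GMR could go either way: a relative rise in the P4M3 baseline overstates the reduction, and a fall understates it. The multipliers of 0.79 to 1.22 rest wholly on assumed f and b and are not an estimate.

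Two stronger readings are tempting. One is that the bias always favours P4M3; that follows only if subjects about to give up cigarettes smoke more, and nothing in the documents establishes it. The other is that every confirmatory model is compromised; COHb is not exposed, because its baseline sample is listed before randomization. Randomizing during Day -1 is not in itself the defect, provided the arm is withheld from subjects. Sample size, nominal alpha and stated power are unchanged. The correction should be made because it protects the main estimate at almost no cost.

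**What to change.** 1. Delete the disclosure row from Table 11, leaving Table 12 (Day 1, after completion of the Day -1 urine collection) as the only disclosure point.
2. Add to Protocol 6.3 and SAP 4.6.1 that, whenever on Day -1 the IxRS randomization is done, the allocation is not released to subjects until the Day -1 urine collection is closed. On schedule this fits the existing clock times, since baseline ends at 06:29 AM and exposure starts at 06:30 AM.

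The cost is a wording change in two documents, with no added procedure and no change to sample size or alpha. Moving randomization to after 11:00 PM and reordering the questionnaires are not required. If any cohort has already run under Table 11, comparing recorded disclosure times with the end of the Day -1 collection would show whether its baselines were exposed.
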